4.2 Endpoint Analyses

This section covers details related to the endpoint analyses such as primary, secondary, other endpoints including sensitivity and supportive analyses.

4.2.1 Primary Endpoint

4.2.1.1 Definition

The primary endpoint is the proportion of patients with an ICS-based maintenance and/or reliever treatment, which is indicated by whether or not the treatment option includes ICS-containing medication. Change from baseline in the proportion of patients with an ICS-based maintenance and/or reliever treatment at week 48 will be analysed.

Doctor's prescription will be used to define this endpoint. The baseline and following analysis visits' definitions refer to section 4.1.9.

4.2.1.2 Primary Analysis of Primary Endpoint

Proportion of patients with an ICS-based maintenance and/or reliever treatment will be described using the frequency with ICS and corresponding percentage at baseline and week 48.

The primary analysis will use mixed effect logistic regression model, taking the measurement timepoint (baseline/post-baseline) as the fixed effect, hospital, pulmonologist and patient as the random effects. Logit link function will be used, and the model parameters will be estimated by maximum likelihood approach. The compound-symmetry variance-covariance structure will be used. In case of lack of convergency, hospital and prescriber factors will be removed from the model.

Within the framework of this model, first predict for all patients the probability of ICS usage at baseline/ post-baseline and then take the average over baseline/ post-baseline patients to get an estimate of proportion, and finally take the difference between the two proportions as the risk difference estimate, the 95% confidence interval of risk difference in proportion by bootstrapping method will be estimated and presented. Besides, Odds Ratio and P value from the model will also be estimated and presented. The analysis will be performed in FAS. Reference SAS code is shown in section 7.

If medication is taken at least once within 3 months before Visit 0 (week -12), the patients will be regarded as taking this medication at baseline. For Visit 2 (week 12), if medication is taken at least once on or after Visit 1 and on or before Visit 2 (within 3 months before this visit), the subjects will be regarded as taking medications at this visit. For Visit 3 -Visit 5 (week 24, 36 and 48), if medication is taken at least once after last visit and on or before this visit (within 3 months before this visit), the subjects will be regarded as taking medication at this visit.

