9 STATISTICAL CONSIDERATIONS

9.1 Statistical Hypotheses

The change in GINA guideline-recommended treatment after guideline education and implementation, will be compared between the proportion of patients on with an ICS-based maintenance and/or reliever treatment at Week 48 and the proportion at baseline. For each treatment arm, the proportions along with the 95% confidence intervals the rates and the difference Δ will be computed. The hypothesis test is formed as follows:

The null hypothesis to be tested is:

H_0 : Proportion of patients with ICS-based maintenance and/or reliever treatment at baseline =
Proportion of patients with ICS-based maintenance and/or reliever treatment at Week 48

Against the alternative hypothesis:

H_a : Proportion of patients with ICS-based maintenance and/or reliever treatment at baseline \neq
Proportion of patients with ICS-based maintenance and/or reliever treatment at Week 48

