1.3 Number of Subjects

Approximately 1500 participants will provide 80% power at a significant level of 0.05 to detect a change from baseline in the proportion of patients with an ICS-based maintenance and/or reliever treatment at week 48 of 5%. The baseline proportion is assumed to be 40% and a within-participants correlation is assumed to be 0.25. The proportion of missing postbaseline assessment at week 48 is assumed to be 30%.

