7 APPENDIX

7.1 SAS sample code for proc GLIMMIX

```
proc GLIMMIX data=ics;  
  
class visit (ref='0') hosp doct;  
  
model mpd = visit / dist=binary link=logit oddsratio solution;  
  
contrast 'week 48 vs baseline' time [1,4][-1,5] ;  
  
random subjid hosp doct;  
  
run;
```

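### The SAP does not settle which visits enter the primary mixed model; if all five do, the compound-symmetry P value can exceed its nominal 5% error

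*SAP*

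**What the plan says.** Protocol 9.1 states one two-sided hypothesis, comparing "Proportion of patients with ICS-based maintenance and/or reliever treatment at Week 48" with the same proportion at baseline.

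SAP 4.2.1.2 tests it with a logistic mixed model fitted by maximum likelihood. Timepoint is the fixed effect (baseline versus post-baseline), and hospital, pulmonologist and patient are random. On the covariance it says "The compound-symmetry variance-covariance structure will be used". The risk difference gets a bootstrap interval, and then: "Besides, Odds Ratio and P value from the model will also be estimated and presented". No empirical variance is specified for that P value, and the resampling unit of the bootstrap is not stated.

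The sources differ on which records enter:

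- The text of SAP 4.2.1.2 describes the data at baseline and week 48 and takes the difference of two proportions. Weeks 12, 24 and 36 belong to a separate secondary endpoint (SAP 4.2.2.4).
- The sample code in SAP 7.1 fits a visit factor and has the line "contrast 'week 48 vs baseline' time [1,4][-1,5]". Levels 4 and 5 exist only if at least five visits are in the data. SAP 4.1.9 defines treatment status at exactly five occasions: V0 and weeks 12, 24, 36 and 48.

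SAP 1.3 gives a single correlation: "The baseline proportion is assumed to be 40% and a within-participants correlation is assumed to be 0.25". Nothing is said about how it changes with the time between visits.

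**The concern.** A random-intercept model with compound symmetry gives every pair of visits the same within-patient correlation. The stated null says nothing about correlations, only that two proportions are equal. If five visits are modelled, the reference distribution of the P value also assumes that ICS status 60 weeks apart (V0 at week -12 to week 48) is as strongly related as status 12 weeks apart.

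The documents give reason to doubt this. The post-baseline status windows in SAP 4.1.9 follow one another without a gap. The baseline window closes at V0, the weeks between V0 and V1 belong to no window, and the training, which is meant to change prescribing, starts between V0 and the later windows. The correlation of V0 with week 48 may therefore be lower than the average the model estimates. The standard error of the week-48 change would then be too small.

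At stake is the one P value attached to the primary hypothesis. It could fall below 0.05 beside a bootstrap interval that includes zero, and the SAP does not say which governs.

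**Working it through.** **1. Reproducing the plan's sample size.** Inputs from SAP 1.3: "Approximately 1500 participants will provide 80% power at a significant level of 0.05", 40% to 45%, correlation 0.25, 30% missing at week 48. Using all baselines and the 70% observed at week 48:

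N = (1.96 + 0.8416)² × [p1q1 + p2q2/0.7 − 2ρ√(p1q1·p2q2)] / 0.05²

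= 7.849 × [0.2400 + 0.3536 − 0.1219] / 0.0025 ≈ 1481

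Power at 1500 is about 80.5%, so the plan's figure is reproduced. A completers-only version gives 1148/0.7 = 1640 and does not match. The plan's 0.25 thus works as the correlation of baseline with week 48, and it is held there below.

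**2. Two visits only.** One pair has one correlation, so compound symmetry imposes nothing. Ratio of true to model standard error: 1.000. Type I error: 5.0%, whatever the correlation.

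**3. Five visits, hand approximation (no missing data).** The variance of a within-patient difference is proportional to 1 − ρ. The truth uses the V0-to-week-48 correlation, 0.25. The model uses roughly the average ρ̄ over the ten pairs. So

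k = true SE / model SE ≈ √[(1 − 0.25)/(1 − ρ̄)], and type I error = 2[1 − Φ(1.96/k)].

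- Equal correlations: ρ̄ = 0.25, k = 1, error 5.0%.
- 12-week correlation 0.50: ρ̄ = 0.373, k = √(0.75/0.627) = 1.094, error 7.3%.
- First-order decay: the 12-week correlation is 0.25^(1/5) = 0.758, ρ̄ = 0.545, k = √(0.75/0.455) = 1.284, error 12.7%.

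**4. Five visits, fitted model.** A random-intercept logistic model was fitted by maximum likelihood (60-point quadrature). ICS use was 40% at every visit (null true), with visits at weeks -12, 12, 24, 36 and 48 and missingness at random rising to 30% at week 48. k is the sandwich SE over the model SE for week 48 versus baseline. Hospital and pulmonologist effects were left out, as in the SAP's own non-convergence fallback. The 12-week correlation is an assumption and is varied.

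| Pattern (V0 to week 48 = 0.25) | 12-week correlation | k | Type I error |
|---|---|---|---|
| Equal for all pairs | 0.25 | 1.000 | 5.0% |
| Falling and levelling off | 0.35 | 1.024 | 5.6% |
| | 0.40 | 1.040 | 6.0% |
| | 0.45 | 1.061 | 6.5% |
| | 0.50 | 1.085 | 7.1% |
| | 0.60 | 1.150 | 8.8% |
| First-order decay | 0.758 | 1.263 | 12.1% |

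Other shapes: a linear decline from 0.4-0.7 to 0.25 gives 6.5-11.9%. If V0 has 0.25 with every later visit and only the later visits are more strongly related to each other, the error is 6.1-8.3%.

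**5. Simulation at N = 1500 (2000 runs).** The model-based P value rejects 5.4% of the time with equal correlations, 6.3% at a 12-week correlation of 0.40, and 13.1% under first-order decay (Monte Carlo SE 0.75 points). On the first-order data, patient-level sandwich errors from the same fit reject 5.6%, and a robust marginal contrast 6.0% (Monte Carlo SE about 0.5 points).

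**The case against.** The strongest reply is that the plan may never fit five visits. The hypothesis, the descriptive sentence and the two-proportion difference all name baseline and week 48 only. The sole evidence for five is sample code that would need correcting anyway: the contrast refers to a term, time, that is not in the model, and the patient identifier is a random effect but is missing from the class statement. This stands. Text and code conflict, and the text read alone gives a valid test. What does not follow is that the matter can be left, because no sentence limits the records to those two visits.

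A reader might infer that the primary test is known to reject a true null 7-12% of the time. The documents do not support that. They give one correlation and no decay pattern, and mild differences give about 5.5-6.5%. Nor is 12% a ceiling for every input: under first-order decay, a V0-to-week-48 correlation of 0.10 gives 10.0% and of 0.60 gives 14.6%. The full model with hospital and pulmonologist effects was not simulated.

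A two-level factor that pools all post-baseline visits would also be affected (12.0% under first-order decay), but it would not test week 48.

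Finally, the plan has partial safeguards: the bootstrap interval and the GEE sensitivity analysis. A bootstrap over whole patients, or a GEE with empirical errors, would not carry the fault. The SAP states neither the resampling unit nor the GEE variance, so this protection is likely but not assured, and it does not reach the primary P value.

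**Conclusion.** The point holds conditionally. What the documents establish is an inconsistency over which visits enter the primary model, together with a P value that relies on compound symmetry and has no robust variance.

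The consequence depends on how the inconsistency is resolved. With baseline and week 48 only there is no fault. With five visits, a V0-to-week-48 correlation of 0.25 and 30% missing, the error is about 5% if correlations are equal, about 6-8% for a mild to moderate difference, and up to about 12% under first-order decay. These figures assume data missing at random and no hospital or pulmonologist effects. The decay itself is assumed, not documented.

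This merits a change before the analysis because the change is cheap. It is not proof that the planned test is invalid.

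**What to change.** In SAP 4.2.1.2, state which visits enter the primary model, and make the SAP 7.1 code agree, including the contrast term and the class statement. Then choose one of two routes:

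1. Restrict the primary model to baseline and week-48 records. Compound symmetry is then harmless. The cost is the loss of the information in the intermediate visits.
2. Keep all visits, and use the mixed model for the point estimate only. Take the P value and the odds-ratio interval from the planned bootstrap, resampling whole patients or larger clusters so that all of a patient's visits stay together. Alternatively, use empirical (sandwich) standard errors clustered at least by patient. Remove compound symmetry as the basis for inference.

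In either case, put the P value and the risk-difference interval on the same basis, and state the bootstrap unit.

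The cost is SAP wording and a little code, since the bootstrap is already planned. Under route 2 the P value is slightly less favourable if correlation declines. With equal correlations there is practically no loss (SE 0.096 on the logit scale either way). The sandwich option should be tried in the full model with about 30 hospitals before it is adopted, because it was checked here only without those effects.

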6 STUDY INTERVENTION

6.1 Study Intervention – Quality Improvement Program

The intervention of Quality Improvement Program (i.e., GINA guideline education/training and implementation) will be delivered at the hospital level, targeting all pulmonologists and specialist nurses at participating hospitals, as illustrated in Figure 1. A scientific steering committee will be established and responsible for the overall quality and successful implementation of the QIP.

Figure 1 Study Design

The guideline education/training part includes pulmonologist-targeted GINA 2021 based initial comprehensive education and regular reinforcement learning (including but not limited to guideline training reinforcement, targeted education based on guideline implementation assessment and feedback, and case discussion). If GINA is updated, the updated content will also be delivered in educational interventions. The investigator information will be collected and analysed, including job category (doctor or nurse), age, years of work experience,

professional title, education background, assessment of inhaler skill score, etc.

The guideline implementation part focuses on regular assessment and feedback on guideline adherence performance in practice. The feedback will be used to guide QIP adjustment, e.g., reinforcement learning.

Multiple online and offline approaches serving as reminders and supportive tools to the QIP. The online approach will also facilitate pulmonologists and specialist nurses to manage their patients.

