The intervention will be targeting pulmonologists at site hospitals. To reflect the real world practice, all pulmonologists attending outpatient clinics will be expected to recruit patients. However, depending on the scale of the selected hospitals and actual study operation, the number of participating pulmonologists will vary, as well as the number of pulmonologists who recruit patients, and the number of patients recruited per pulmonologists. These variations may introduce biases into this study. During the study conduct, patient recruitment will be closely monitored for unusual pattern. In addition, the statistical analyses will take into account the within-hospital and within-pulmonologist correlation, by including the hospital and pulmonologist effect into the model as random effect.

Retrospective data based on electronic medical records (EMR) offers a potential source of data collection. However, the original purpose of collecting EMR is for clinical care

management rather than research purpose, so there are inherent limitations in using EMR data to conduct clinical research, e.g., information incompleteness and data inaccuracy. Some data required by the protocol, e.g., ACQ-5 and AQLQ(S)+12, are not routinely collected in clinical practice. As this is a pragmatic study, patients can potentially go to any hospitals or pulmonologists for care during the study and EMR data from site hospitals will not be able to capture all the information. Given these inherent limitations of EMR data, we choose to prospectively collect data from patients in this study.

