9.2 Sample Size Determination

Approximately 1500 participants will provide 80% power at a significant level of 0.05 to detect a change from baseline in the proportion of patients with an ICS-based maintenance and/or reliever treatment at week 48 of 5% (Zhao et al 2014). The baseline proportion is assumed to be 40% and a within-participants correlation is assumed to be 0.25. The proportion of missing postbaseline assessment at week 48 is assumed to be 30%.

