9.4.2 Effectiveness

9.4.2.1 Primary Endpoint(s)

Change from baseline in the proportion of patients with an ICS-based maintenance and/or reliever treatment at week 48

Prescription will be used to define this endpoint. The primary analysis will use mixed effect logistic regression model, taking the measurement timepoint (baseline/post-baseline) as the fixed effect, hospital, pulmonologist and patient as the random effects. In case of lack of convergency, hospital and pulmonologist factors will be removed from the model. Within the framework of this model, the 95% confidence interval and p value of the primary endpoint will be estimated and presented. The analysis will be performed in FAS.

Another sensitivity analysis will be conducted with generalized estimating equations (GEE) model using the same covariates as the primary analysis.

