1.2 Study Design

The study will select a total of around 30 Tier 2 and Tier 3 hospitals across China and enrol approximately 1500 asthma patients ≥ 14 years old with all severities from the 30 participating hospitals. To represent the real-world situation of patients, pulmonologists and treatment practice, hospital selection will include as many as provinces or municipalities in mainland China, where the altitude is below 1,500 meters, while balancing hospital grade (e.g. 10 Tier 2 and 20 Tier 3). Patients will be recruited in hospital outpatient setting, where all potentially eligible asthma patients will be consecutively approached and invited to join the study, e.g., regardless of new patients or treated, exacerbation or regular follow-up.

The QIP (i.e., GINA 2021 guideline education/training and implementation) will be delivered to pulmonologists and specialist nurses in participating hospitals at hospital level, including pulmonologist-targeted initial comprehensive education based on GINA 2021, guideline implementation performance assessment and feedback, reinforcement learning, along with multiple online and offline approaches serving as reminders and supportive tools to ensure consistent education and to facilitate the asthma management in daily clinical practice in accordance with GINA 2021 recommendation.

Immediately after last patient has been enrolled at each site, the study intervention will be initiated, i.e., the initial comprehensive training on GINA 2021 will be offered to pulmonologists and specialist nurses in this hospital. All successfully enrolled participating patients will be followed up for up to 48 weeks and return to recruiting hospital for study

visits every 12 weeks. The total participating duration in this study for each participating patient will be approximately 60 weeks.

The study aims to bridge the gap between the recommendations from GINA 2021 and current clinical practice via an asthma QIP (including GINA guideline education/training and implementation).

Figure 1 Study Design

[figure not shown]

Table 1 Schedule of Activities (participating patients related)

Study Visit	Baseline Period	Intervention Period					Details in CSP Section or Appendix
		V0	V1	V2	V3	V4	
Study Visit							
Weeks		-12 ±7	0 ±14	12 ±7	24 ±7	36 ±7	48 ±7
Informed consent ^a	X						
Inclusion and exclusion criteria	X						Sections 5.2.1 and 5.2.2
Demographics ^b	X						
Vital Sign ^c	X						
Subject status ^d	X						
Smoking status ^e	X						

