4.2.1.3 Sensitivity Analyses of the Primary Endpoint

Sensitivity analysis will be conducted with generalized estimating equations (GEE) model using measurement timepoint (baseline/post-baseline) as the fixed effect, and subject ID is used to identify individual subjects. Reference SAS code is shown in section 7. Logit link function will be used for binary distribution. The model parameters are estimated by generalized estimating equations. Compound-symmetry working correlation matrix will be used to model the correlation of the responses from subjects.

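### If the primary model does not converge, the fallback drops hospital together with pulmonologist; where week-48 retention is related to a hospital's ICS level, this can bias the odds ratio and p-value (minor)

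*SAP*

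**What the plan says.** SAP 4.2.1.2 fits a mixed logistic model with timepoint as the fixed effect and "hospital, pulmonologist and patient as the random effects". The fallback in the same section is "In case of lack of convergency, hospital and prescriber factors will be removed from the model". Protocol 9.4.2.1 has "In case of lack of convergency, hospital and pulmonologist factors will be removed from the model", and the statistical part of the synopsis repeats the rule. Both levels go in one step, there is no intermediate model, and non-convergence is not defined. The patient effect stays.

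The programme "will be delivered at the hospital level, targeting all pulmonologists and specialist nurses at participating hospitals" (protocol 6.1), at around 30 hospitals with about 1500 patients in all (SAP 1.2). Protocol 6.7 notes that the number of patients per pulmonologist will vary. As mitigation it promises that "the statistical analyses will take into account the within-hospital and within-pulmonologist correlation", through random effects.

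In the GEE sensitivity analysis (SAP 4.2.1.3) timepoint is the only covariate and "subject ID is used to identify individual subjects". The code in SAP 7.2 names hospital and doctor as class variables but uses neither in the model statement.

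On missing data, protocol 9.2 assumes 30% missing at week 48 and SAP 3.1.7 does not impute. The FAS (SAP 4.1.2) requires any one post-intervention treatment assessment, which need not be at week 48.

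**The concern.** After the fallback, no model of the primary endpoint contains hospital, the level at which the programme is delivered. Patients without a week-48 value can stay in the FAS on an earlier visit, so their baselines enter unpaired. If hospitals that prescribe more ICS also retain more patients, the week-48 sample leans towards those hospitals while the baseline sample represents all of them. A model with only a patient intercept reads part of that shift in mix as change. If the link runs the other way, it hides or reverses change. A hospital term compares like with like and removes most of the effect.

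The odds ratio and p-value that would be reported as the primary result are at stake, in a situation the plan itself foresees. Pulmonologist is the sparser level. Hospital, at about 1500/30 = 50 patients each, is the easier one to keep. The rule discards both.

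**Working it through.** **1. The plan's sample size.** Inputs from protocol 9.2 and SAP 1.3: 40% to 45%, within-patient correlation 0.25, 30% missing at week 48, 80% power; two-sided 5% from the hypotheses in protocol 9.1.

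n = (1.960 + 0.842)² × [0.24 + 0.2475/0.70 − 2 × 0.25 × √(0.24 × 0.2475)] / 0.05² = 7.849 × 0.4717 / 0.0025 ≈ 1481.

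This agrees with the stated 1500, at which power is 80.5%. The formula keeps unpaired baselines, as the planned model does. No hospital term enters it.

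**2. Mechanism, with no true change.** Take two equal halves of hospitals with ICS use 50% and 30% (40% overall). With dropout 10% and 50% (30% overall), the high-ICS half makes up 0.9/1.4 = 64.3% of week-48 patients, so the observed proportion is 0.643 × 50 + 0.357 × 30 = 42.86%. That is a raw shift of +2.86 points. Large-sample maximum-likelihood fits of the patient-only model give:

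| Dropout in high-ICS / low-ICS half | Raw shift (points) | Baseline and week 48 only | All visits modelled |
|---|---|---|---|
| 30% / 30% | 0 | 0 | not run |
| 20% / 40% | +1.43 | +1.07 | +0.61 to +0.86 |
| 10% / 50% | +2.86 | +2.15 | +1.22 to +1.71 |
| 50% / 10% | −2.86 | −2.16 | not run |

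The retained patient effect absorbs about 25% of the shift with two timepoints, and about 40% to 57% when earlier visits are modelled.

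**3. Size across 30 hospitals.** Assumptions, none of them in the documents: hospital ICC 0.05 to 0.10, retention mean 70% with SD 15 points, retention-ICS correlation 0.5 to 0.8, no hospital-by-time variation. With two timepoints:

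spurious change ≈ (1 − 0.25) × correlation × 0.15 × √(ICC × 0.24) / 0.70

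- ICC 0.05: √0.012 = 0.1095, giving 0.9 points (correlation 0.5) and 1.4 points (0.8).
- ICC 0.10: √0.024 = 0.1549, giving 1.2 and 2.0 points.

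For all visits, replace 0.75 by 0.60 to 0.43. The smallest case becomes 1.17 × 0.60 = 0.70 to 1.17 × 0.43 = 0.50, about 0.6 points. The largest becomes 2.66 × 0.60 = 1.6 to 2.66 × 0.43 = 1.1 points.

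**4. False-positive rates** (nominal 5%, 30 hospitals of 50 patients, every patient missing week 48 kept in the FAS):

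| ICC, correlation | Two timepoints, patient only | Two timepoints, hospital kept | Second run: two timepoints, patient only | Second run: five visits, patient only |
|---|---|---|---|---|
| 0.05, 0.5 | 8.0% | 5.1% | 6.6% | 5.9% |
| 0.05, 0.8 | 11.8% | 5.4% | 10.3% | 6.5% |
| 0.10, 0.5 | 11.3% | 4.6% | 9.1% | 6.5% |
| 0.10, 0.8 | 19.1% | 4.8% | 14.9% | 8.5% |

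The first two columns used 3000 replicates per cell and the last two 1500. A linear generalised-least-squares approximation (400 runs per cell) gave about 9% to 21% with two timepoints and 7% to 11% with five visits, against about 3% to 6% with hospital kept. Together these give about 7% to 21% and about 6% to 11%. With retention unrelated to hospital ICS level, the first simulation gave 5.9% without hospital and 5.7% with it.

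**5. Risk difference.** SAP 4.2.1.2 averages predicted probabilities over the baseline and the post-baseline patients. If those are the patients observed at each timepoint, the result equals the raw difference in observed proportions whether or not hospital is in the model. In simulated examples with a hospital SD of 0.45 on the logit scale, both models gave +1.0 and +2.3 points. Keeping hospital therefore protects the odds ratio and p-value, but not this version of the risk difference.

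**The case against.** - **The harm is conditional twice over.** It needs non-convergence, whose probability cannot be estimated from the documents, and a link between retention and hospital ICS level, on which they are silent. A reader might infer that differences in dropout between hospitals are enough to create apparent change. They are not: unequal dropout unrelated to ICS level does no harm. This stands and limits the claim.
- **The largest rates need a two-timepoint model.** The contrast in SAP 7.1 puts coefficients on levels 4 and 5 of the visit factor, which implies five visits. The text's baseline/post-baseline wording leaves the other reading open, so both are shown. If half of those missing week 48 also leave the FAS, the five-visit rates fall to 5.3%, 5.2%, 6.1% and 7.0%.
- **Hospital is not wholly ignored.** Its variance moves into the patient intercept, and patients with both values still cancel their hospital's level. This is correct, and the figures above already include it.
- **Planned analyses might show the problem.** SAP 4.2.4 lists subgroups by hospital tier, by region and by missing or not missing week 48. A reader might infer that nothing planned could detect the bias, which goes too far. But these subgroups are exploratory and optional, and would not correct the primary result.
- **Pulmonologist as the cause of failure is not shown.** It is the sparser level, which makes it the natural one to remove first. The documents do not establish more.

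**Conclusion.** The point stands as a minor one. The fallback removes a level that protocol 6.7 relies on, and no supporting model of the primary endpoint restores it. Under the assumptions in step 3 and no true change, the patient-only model has a false-positive rate of about 7% to 21% with two timepoints and about 6% to 11% with all visits, against about 5% with hospital kept. The spurious change is about 0.6 to 2.0 points against a 5-point target, and its sign may be positive or negative. With no link between retention and hospital ICS level there is no effect.

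A reader might infer that the planned primary analysis is itself biased. For the odds ratio and p-value the documents do not support that: the full model contains hospital, and the issue arises only if it fails to converge. The averaging behind the risk difference needs attention in either case (step 5). Variation between hospitals in the size of the change is a separate matter, which a hospital intercept does not address.

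**What to change.** In SAP 4.2.1.2, protocol 9.4.2.1 and the synopsis, replace the fallback sentence with an ordered rule:

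1. If the model does not converge, remove the pulmonologist random effect and keep hospital and patient.
2. If it still does not converge, enter hospital as a fixed effect and keep patient random.
3. Do not remove hospital from the primary model.

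State what counts as non-convergence. Add hospital as a covariate to the GEE in SAP 4.2.1.3 and to the code in 7.2. Specify that the risk difference averages predictions at both timepoints over the same FAS patients.

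The cost is a few sentences and a small change of code, with no new data or patients. The downside is up to about 30 fixed hospital terms in the last step, with about 50 patients per hospital to support them. The rule should be fixed before the week-48 results are seen.

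### The SAP does not say how random effects enter the averaged predictions behind the primary risk difference; under maximum likelihood, the two usual plug-in choices overstate the change in proportion

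*SAP*

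**What the plan says.** SAP 4.2.1.1 defines the primary endpoint as a change from baseline to week 48 in the proportion of patients on ICS-containing treatment. Protocol 9.1 puts the two-sided hypothesis, and the difference to be computed, in terms of the same two proportions.

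SAP 4.2.1.2 specifies a logistic mixed model "taking the measurement timepoint (baseline/post-baseline) as the fixed effect, hospital, pulmonologist and patient as the random effects". On fitting it says "Logit link function will be used, and the model parameters will be estimated by maximum likelihood approach". For the effect size the instruction is to "first predict for all patients the probability of ICS usage at baseline/ post-baseline and then take the average over baseline/ post-baseline patients", then subtract, with a bootstrap confidence interval. The odds ratio and p-value come directly from the model. Observed frequencies and percentages at both timepoints are also tabulated.

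Nothing in 4.2.1.2 says what value the random effects take in the prediction. The GLIMMIX sample code in section 7.1 names no estimation method and requests no predicted values.

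The sensitivity analysis in 4.2.1.3 is a GEE, for which "Logit link function will be used for binary distribution". Neither that section nor the code in 7.2 names a risk difference as an output. Section 4.2.1.4 plans no supplementary analysis.

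**The concern.** A logistic mixed model describes probabilities conditional on the patient. Because the logit is non-linear, evaluating the inverse logit at a single value of the random effect and averaging over patients does not in general return the proportion of patients on ICS, even with complete data. This holds for both common plug-in predictions under maximum likelihood: random effects at zero, and random effects at their empirical-Bayes modes. Both sit too near the steep middle of the curve, so a given shift on the logit scale turns into too large a difference in probability.

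What is at stake is the size of the headline effect. The point estimate would answer a different question from the endpoint definition. The bootstrap interval would be built around the same wrong quantity, since resampling a biased estimator does not remove its bias. The model-based proportions would also disagree with the observed percentages reported beside them.

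**Working it through.** **Inputs.** SAP 1.3 (the same figures are in Protocol 9.2): "Approximately 1500 participants will provide 80% power at a significant level of 0.05"; "The baseline proportion is assumed to be 40% and a within-participants correlation is assumed to be 0.25"; a change of 5 points; "The proportion of missing postbaseline assessment at week 48 is assumed to be 30" percent. The test is two-sided, from Protocol 9.1.

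**1. Reproduce the plan's figure.** Use all baseline values and 70% of week-48 values:

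N = (1.960 + 0.842)² × [0.40×0.60 + 0.45×0.55/0.7 − 2×0.25×√(0.24×0.2475)] / 0.05²
= 7.849 × (0.2400 + 0.3536 − 0.1219) / 0.0025 = 1,481.

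This agrees with about 1,500, where power is 80.5%. So 40%, 45% and 0.25 are marginal quantities, and the true change on the plan's scale is 5.0 points.

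**2. Find the matching mixed model.** Take logit P(Y_t = 1 | u) = β_t + u, with u normal with mean 0 and variance σ², and a patient effect only. Solving by quadrature for marginal proportions 0.40 and 0.45 and correlation 0.25 gives β_0 = −0.542, β_48 = −0.269 and σ = 1.327 (σ² = 1.76). Check: P(ICS at both times) = 0.2409, and (0.2409 − 0.18)/√(0.24×0.2475) = 0.25.

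**3. Random effects at zero.** expit(−0.542) = 0.368 and expit(−0.269) = 0.433. The difference is 0.0655, and 0.0655/0.0500 = 1.31, so +31%. Every patient gets the same prediction at a given timepoint.

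**4. Empirical-Bayes modes.** For each response pattern, solve Σ(y − expit(β + u)) = u/σ².

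| Baseline, week 48 | Probability | Mode | Predicted, baseline | Predicted, week 48 |
|---|---|---|---|---|
| no, no | 0.391 | −0.809 | 0.206 | 0.254 |
| no, yes | 0.209 | 0.189 | 0.413 | 0.480 |
| yes, no | 0.159 | 0.189 | 0.413 | 0.480 |
| yes, yes | 0.241 | 1.142 | 0.646 | 0.705 |

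The weighted averages are 0.3879 and 0.4460, difference 0.0581 (+16%).

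Patients with week 48 missing have modes −0.469 (baseline no) and 0.777 (baseline yes), with average predictions 0.3834 and 0.4438. With 30% missing completely at random, the averages over all patients are 0.7×0.3879 + 0.3×0.3834 = 0.3866 and 0.7×0.4460 + 0.3×0.4438 = 0.4453, difference 0.0588 (+18%). If the week-48 average covers only patients seen at week 48, the difference is 0.4460 − 0.3866 = 0.0594 (+19%).

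**5. Integrated or posterior-mean predictions.** Integrating expit(β_t + u) over the normal distribution returns 0.400 and 0.450, difference 0.0500. Averaging each patient's posterior-mean probability gives the same by iterated expectation. There is no bias.

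**6. Departures from the simple model.**
- Hospital or pulmonologist variance. The documents give no split. Assuming that 10% to 50% of the variance is at that level, modes overstate by about 17% down to 9%.
- More visits. With baseline and four post-baseline visits in the model and full follow-up, modes give 0.0551 (+10%). The contrast line in section 7.1 refers to a fourth and a fifth time level, so a multi-visit fit is possible.
- Pseudo-likelihood fit with BLUP predictions. The difference is 0.0497 to 0.0500, essentially no bias. Pseudo-likelihood with random effects at zero gives +2% to +12% for variances of 0.5 to 1.76.

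**7. Simulation check.** In 300 maximum-likelihood fits with N = 1,500 and 30% missing, the mean integrated difference was 0.0518, modes gave 0.0608 to 0.0616, and zero gave 0.0679. Relative to the integrated value these are +17% to +19% and +31%.

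**8. Odds ratios.** Conditional: exp(−0.269 + 0.542) = 1.31. Marginal: (0.45/0.55)/(0.40/0.60) = 1.23. The mixed-model and GEE odds ratios differ by construction.

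**The case against.** The strongest reply is that the SAP does not prescribe a biased estimator. It asks for predicted probabilities averaged to a proportion, and integrated or posterior-mean predictions fit those words and are unbiased. This stands. A reader might infer that the primary risk difference is certain to be wrong by a fixed percentage; the documents do not support that, because the prediction type is left open.

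A reader might also take +31% as the patient-level figure. It is not: it belongs to random effects at zero, where there is nothing to average over patients. The patient-level figure from the plan's inputs is +16% to +19%, and it comes from a patient-only model, whereas 4.2.1.2 also plans hospital and pulmonologist effects. Step 6 shows that these reduce the overstatement without removing it.

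A further reply is that the sample code names no method, and that a pseudo-likelihood fit with BLUP predictions would be close to unbiased. The arithmetic is right, but the text specifies maximum likelihood. The gap between text and code is a reason to align them, not a safeguard.

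It would also go too far to say that the GEE reports only an odds ratio or is of no use as a check. Section 4.2.1.3 names no reported quantity, the marginal proportions follow directly from the GEE coefficients, and the GEE can check direction and significance. But no risk difference is planned from it.

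Finally, the test is untouched, and the observed percentages would expose a gap. Both are true. With the plan's inputs the standard error of the change is √(0.4717/1500) = 0.0177, so the 95% half-width is about 3.5 points. A bias of 0.8 to 0.9 points is about a quarter of that: modest, but in the headline figure.

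**Conclusion.** The concern holds as a gap in specification with a real numerical consequence. On the plan's own assumptions, the same data and model can report a 5-point change as anything from 5.0 to about 6.5 points, depending on a programming choice that the SAP does not state.

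- Patient effect only, maximum likelihood: +16% to +19% with modes, +31% with random effects at zero.
- Part of the variance at hospital or pulmonologist level (shares assumed), or all visits in the model: about +9% to +17% with modes.
- Integrated or posterior-mean predictions: none. Pseudo-likelihood BLUPs: about none.

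These figures rest on a normal random intercept and, where data are missing, on missingness completely at random. The model p-value and odds ratio are not affected. The risk difference and its bootstrap interval are.

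**What to change.** - **SAP 4.2.1.2:** state that each proportion is the predicted probability integrated over the estimated random-effects distribution (population-averaged), for the same FAS patients at both timepoints, and that the integration is repeated in every bootstrap replicate.
- **SAP 7.1:** make the code match the maximum-likelihood text, and add the step that produces the integrated probabilities.
- **SAP 4.2.1.3 and 7.2:** also report the GEE population-averaged risk difference with its confidence interval, so that the primary and sensitivity results are on one scale.

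The cost is a few sentences and a few lines of code. No new data, visits or change of sample size are needed.
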